***Note: If the study involves a school district, approval must be obtained from the school district.**

Vulnerable Populations:

Not applicable
 Children
 Pregnant women
 Prisoners
 Adults who lack ability to consent
 Employees
 Other, describe: _____

If vulnerable populations will be used, please describe additional safeguards to protect their rights and welfare:

N/A

Recruitment Method (all flyers, advertisements, etc. are subject to IRB review):

- Telephone solicitation (attach script)
- Radio (attach script)
- Television (attach script)
- Newspaper advertising (attach ad copy)
- Posted notices (attach copy)
- Letter (attach copy)
- E-mail (attach copy of text to be sent for recruitment)

Direct person-to-person contact, describe: _____
We will inform the student counseling center about the study and provide referral information

Other, describe: _____

How will initial contact be made with potential participants? (be specific)

Participants will initially be made aware via an email sent to all PVAMU students. For students attending the mental health services at PVAMU, a mental health professional may tell them about the study.

Other than as an Investigator, do you have any other relationship with participants? (i.e. doctor-patient, teacher-student, counselor-student, etc.) Yes No

If Yes, explain the relationship and describe how you will avoid any type of coercion:

It is possible the PI may be a professor of some of the participants. However, no direct contact regarding the study will be made in this relationship capacity and she will not be recruiting participants directly through her courses.

CONSENT

LOCATION

Describe the setting where the consent process will take place (i.e. classroom, office, park, personal computer, etc.):

If the consent is in person, this will take place in [name] office, [name], where [name] will provide a paper version of the consent form that students will sign with a pen. If the consent will take place online via an electronic device such as a phone or computer, participants will receive the consent form via docusign. Through docusign they can sign electronically to indicate their consent.

PERSONNEL

Name individuals or group of individuals who will be speaking directly to potential participants during the consent process:

[name] will be available to participants to answer any questions as they read through the consent form. Her contact information is available on the consent form.

CONSENT TOOLS

Please check all that apply and attach to the application:

 Cover Letter	 Adult Consent Form
 Information Sheet	 Minor Assent Form
 Telephone Script	 Parental Consent Form

Location where consent forms will be filed:

(Consent forms must be kept on file for 3 years after completion of the study and data analysis)

All data and forms including consent forms will be kept on a password protected computer in [name] office in [name]

WAIVER

Request for waiver of informed consent or waiver of documentation of informed consent:

Yes No

If Yes, explain below:

[Large empty box for explanation]

COMPENSATION / COURSE CREDIT

Will monetary compensation be given to the participant?

Yes No

If Yes, explain below and attach a detailed compensation of payment including amount and schedule of payments to participant:

Participants will receive payment in the form of Amazon gift cards. Our study has 4 time points in which participants may be compensated for their time. These time points are listed below along with the amount participants receive for taking part in each time point.

Time	Compensation
Time 1: before therapy started	\$5
Time 2: 4 weeks after therapy has started	\$50
Time 3: 8 weeks after therapy has started	\$100

Will course credit be given to the participant as compensation?

Yes No

If Yes, provide details below and alternate assignment to obtain equal credit:

SUBJECT MATTER

Check the appropriate box(es) concerning the subject matter of the research:

 No sensitive matters	 Learning disability
 Abortion	 Physical disability
 AIDS/HIV	 Psychological inventory
 Alcohol	 Review of criminal records
 Body composition	 Review of educational records
 Criminal activity	 Sexual Activity
 Depression	 Suicide
 Drugs	 Other, specify: general mental health issues

DECEPTION OR COERCION

Will deception or coercion be used?

Yes No

If Yes, attach debriefing form and briefly describe deception:

PROCEDURES

What will participants be asked to do? (Describe the study in detail from recruitment to completion)
If you need additional space, put "see attached" in the box below and attach complete description of procedures.

Participants will access the study via an online link provided by email or via word of mouth. Next, they will take the PHQ-9 and the GAD-7 to measure their depression and anxiety levels. If they score 5 or above on either test they will be invited to participate in the therapy part of the study. In this part of the study the participant will be assigned to either receive individual teletherapy or group teletherapy for 12 weeks. This therapy takes place via text. Participants may be asked to read psychoeducational materials and complete homework assignments. Participants assigned to the individual therapy, will receive support in the form of direct asynchronous communication with the therapist. Participants assigned to the group therapy will receive support in the form of direct asynchronous communication with the therapist and asynchronous communication with peers struggling with similar issues. Throughout the at week 4, 8 and 12 of therapy, participants will take the GAD-7, PHQ-9, and self-report questionnaires to measure their engagement and experience.

Describe the location where research activities will take place:

The research will take place on participants personal electronic devices by logging on to the web-based TheraGroup platform. TheraGroup is a proprietary real-time virtual based platform that provides text based group therapy. It is a cloud software that offers HIPAA compliant asynchronous text chat.

How long will the participants be engaged in research? (*length of time, i.e. 15 minutes on day 1, etc.*):

up to 12 weeks

During data collection, describe what steps will be taken to ensure participant privacy:

Due to the longitudinal design of this project, collecting identifiable data is necessary. Specifically, participants' names and contact information are needed to match participant information at different time points and to contact participants about distributing their gift card compensation. In order to preserve participant confidentiality and minimize the potential harm of participant information being identified, participants' will be prompted to create an identification number comprised of the first two letters of their last name combined with the last four digits of their phone number (e.g., Jane

Is the research anonymous or confidential? (**Cannot be both**)

Anonymous: The identity of the participant cannot be readily determined by the investigator AND the identity of the participant is not connected to information gathered.

Confidential: Research participants can be identified; however, information gathered will be protected.

Provisions for anonymity/confidentiality:

Secure storage (**required**)

Replies coded

What specific steps will be followed to ensure anonymity or confidentiality of participants' responses?

The participant ID and identifying information (name-code-index) as described above will be stored on a password protected spreadsheet. Only [name] and her team will have the ability to de-identify participants. Disclosure of data via research dissemination methods such as presentations at conferences and in study related publications will not contain identifying information. In addition, for the group therapy, participants use a name they make up for the purpose of the group only to ensure they remain anonymous. The therapy contains no face to face modalities. It all occurs via text based communication.

DATA COLLECTION

Research Type:

- Qualitative
- Quantitative
- Both

Will any new data or documents be collected? (i.e. *public records, survey instruments, evaluation tools, etc.*)

- Yes
- No

If Yes, describe what data or documents will be used and how they will be obtained:

Data will include the following: 1. Behavioral data (events that occur in the system due to students interacting with the system; e.g., time spent logged on) 2. Self-report data (measures of engagement, user experience surveys, the PHQ and GAD7 scores). Participant data will be collected via the TheraGroup systems backend in the form of log data (Behavioral Data) or through Qualtrics (Depression and Anxiety scores, measures of engagement, user experience surveys).

Will recordings be made?

- Yes
- No

If Yes:

- Video Taping
- Audio Taping
- Mandatory Recording
- Voluntary Recording

Is the use of recordings detailed in the consent form?

- Yes
- No

Will recordings be retained?

- Yes
- No

If Yes, how long will records be retained before they are destroyed/erased?

Will any new specimens be collected? (i.e. *blood tissue, etc.*)

- Yes
- No

If Yes, describe what specimens will be used and how they will be obtained:

Does the experiment involve the use of human fluid, tissue and/or blood?

- Yes
- No

Will any invasive or sensitive procedures be done?

Yes No

If Yes, check all that apply:

- Blood Samples
- Physical Measurements (electrodes, etc)
- rDNA
- Stress Exercise
- Urine Samples
- Other, specify: _____

DOCUMENT RETENTION

Federal regulations require that human research documents be retained for a minimum of three years AFTER the completion of the study AND data analysis. Some disciplines or granting agencies require longer retention times.

Length of time retained after completion of study and data analysis:

At least three years

Person responsible for data retention (*If you are a student, please list faculty mentor*) & data storage location:

All data will be kept on a password protected computer in [name] office in [name].

OTHER COMPLIANCE ISSUES

If the study involves the use of **animals, infectious biohazards (e.g. blood), and/or recombinant DNA**, it is required that approval be granted for the use of such through the appropriate compliance committee.

SIGNATURE ASSURANCES

PRINCIPAL INVESTIGATOR

I understand Prairie View A&M University's procedures concerning research involving human subjects and **by initialing** below, I certify:

AL I have read The Belmont Report "Ethical Principles and Guidelines for the Protection of Human Subjects of Research" and subscribe to the principles it contains.

AL I accept responsibility for the scientific and ethical conduct of this research study.

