Participants will access the study via an online link provided by email or via word of mouth. They will first answer a question to assess their suicide risk. If they have not had suicidal thoughts in the previous three weeks, they will continue on to the study. If they indicate they have had such thoughts in the prior three weeks, they will be disqualified from the study and a screen will appear with contact information regarding mental health resources. [name] will then reach out to Student Counseling Services and ask them to reach out to the students to follow-up and provide additional support. For those students who continue with the study, they will take the PHQ-9 and the GAD-7 to measure their depression and anxiety levels. If they score 5 or above on either test they will be invited to participate in the therapy part of the study. In this part of the study the participant will be assigned to either receive individual teletherapy or group teletherapy for 12 weeks. This therapy takes place via text. Participants may be asked to read psychoeducational materials and complete homework assignments. Participants assigned to the individual therapy, will receive support in the form of direct asynchronous communication with the therapist. Participants assigned to the group therapy will receive support in the form of direct asynchronous communication with the therapist and asynchronous communication with peers struggling with similar issues. Throughout the at week 4, 8 and 12 of therapy, participants will take the GAD-7, PHQ-9, and self-report questionnaires to measure their engagement and experience.

Describe the location where research activities will take place:

The research will take place on participants personal electronic devices by logging on to the web-based TheraGroup platform. TheraGroup is a proprietary real-time virtual based platform that provides text based group therapy. It is a cloud software that offers HIPAA compliant asynchronous text chat.

How long will the participants be engaged in research? (length of time, i.e. 15 minutes on day 1, etc.):

up to 12 weeks

During data collection, describe what steps will be taken to ensure participant privacy:

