IRB Member:	 YES	 NO	Date: _____
Social/Behavioral Research Course:	 YES	 NO	Date: _____
IRB accepts Alternative Training:	 YES	 NO	Date: _____
	 YES	 NO	Date: _____

Training Reviewer: _____ Date: _____ 7/9/2024

PROTOCOL APPROVAL

(for office use only)

EXEMPT

Declared by: _____ Date: _____

EXPEDITED

Approved - Reviewer 1: _____ [name]. Date: _____ 10/28/2024

Approved - Reviewer 2: _____ Date: _____

FULL REVIEW

Referred for Full Review: _____ Date: _____

Approved: _____ Date: _____

Date of Full Review (attach minutes): _____

Subject: Opportunity to Participate in a Research Project

Dear PVAMU students,

My name is [name] and I am an Assistant Professor in the Psychology Department at PV. I am emailing you to invite you to be part of a research project about virtual group mental health therapy for Black college students. The purpose of the research is to determine how group telehealth therapy compares to individual telehealth therapy.

If you participate in this project, you will be asked to first complete two mental health assessments. You may then be asked to continue the study and take part in a 12-week virtual therapy program. During this 12-week period you will be asked to complete activities related to the therapy, take mental health assessments, and provide feedback on your experience.

If you participate in this study, you may be eligible to earn up to \$305.00 in the form of an Amazon gift card over approximately 12 weeks of your time. Participation is voluntary, but I hope you will choose to be part of this project. *To participate in the study you must be a Black PVAMU college student of 18 years or older.*

For more information, or to sign up, go to [enter study website here] or contact me at [contact].

Thanks,

[name]

PHQ-9

Over the last 2 weeks, how often have you been bothered by any of the following problems?

Scale: 0 = not at all; 1 = several days; 2 = more than half the days; 3 = nearly every day

1. Little interest or pleasure in doing things
2. Feeling down, depressed, or hopeless
3. Trouble falling or staying asleep, or sleeping too much
4. Feeling tired or having little energy
5. Poor appetite or overeating
6. Feeling bad about yourself or that you are a failure or have let yourself or your family down

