Statistical Analysis Plan

Official Study Title: Guided group telehealth to deliver evidence-based therapeutic care to Black college students

NCT Number:

Date of Document: 03/10/2025

Statistical Analysis Plan

To test the primary hypothesis that participants in the Guided Group Telehealth (GGT) condition will experience reductions in depression and anxiety comparable to those in the Individual Telehealth (IT) condition, we will use a mixed-design repeated measures ANOVA. The within-subjects factor will be time (baseline, week 4, week 8, and week 12), and the between-subjects factor will be therapy condition (GGT vs. IT). The dependent variables will be PHQ-9 and GAD-7 scores, measuring depression and anxiety, respectively. Interaction effects will be examined to assess whether changes in symptom severity over time differ between the two conditions. For secondary analyses, we will use independent samples t-tests to compare user engagement and user experience scores between the two conditions at week 12. Descriptive statistics will be used to summarize engagement data, including participation rates, message frequency, and task completion. Additionally, qualitative analysis will be conducted on open-ended responses from the user experience survey to identify common themes related to participants' satisfaction and perceived effectiveness of the intervention. All analyses will be conducted using an alpha level of 0.05, and effect sizes will be reported alongside p-values. If violations of normality or sphericity are detected, appropriate corrections, such as Greenhouse-Geisser adjustments or nonparametric alternatives, will be applied.

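### Follow-up is dated from the start of therapy and not from assignment, so assigned students who never start have no scheduled outcome and the baseline-to-week-12 interval may differ between arms

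*Protocol*

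**What the plan says.** The Protocol's Compensation / Course Credit section defines the time points as "Time 1: before therapy started", "Time 2: 4 weeks after therapy has started" and "Time 3: 8 weeks after therapy has started". The row for the fourth time point is not visible in the text available, and I do not count that as an error.

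The Procedures section gives the same origin for all three follow-ups: "at week 4, 8 and 12 of therapy, participants will take the GAD-7, PHQ-9, and self-report questionnaires". It describes the allocation step as "the participant will be assigned to either receive individual teletherapy or group teletherapy for 12 weeks", with no assignment date, no window for starting and no rule for a student who does not start. The same section caps engagement in the research at 12 weeks, and the recruitment email offers up to $305 "in the form of an Amazon gift card over approximately 12 weeks of your time".

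The SAP states "The within-subjects factor will be time (baseline, week 4, week 8, and week 12" but does not say what the weeks are counted from. It plans a mixed-design repeated measures ANOVA on PHQ-9 and GAD-7, with therapy condition as the between-subjects factor. It names no analysis population and no rule for missing data.

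**The concern.** Allocation happens once, after the entry survey. Starting therapy happens later and may depend on the arm offered and on how the student feels. If the outcome schedule exists only for those who start, the arms are compared on a subset formed after assignment, and that subset need not be balanced.

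A second problem comes from the same rule. The ANOVA treats week 12 as one time level for everyone. With an open-ended gap before therapy, week 12 can lie at different distances from baseline. The entry scores are also the qualifying scores (5 or more on either scale), so some change unrelated to therapy is plausible over that gap.

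The SAP's primary hypothesis is that the group arm does comparably to the individual arm. A distortion of either sign therefore bears directly on the conclusion. Outcomes that were never scheduled cannot be collected after the trial.

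**Working it through.** The plan has no figure to reproduce: the sample size of 200 is a stated maximum with no derivation. The check is a reading of the schedule, followed by illustrative arithmetic in which every rate, gap and wait is an assumption.

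**1. Which clock applies**

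- Baseline: the PHQ-9 and GAD-7 at entry. The documents describe no other baseline, and the payment schedule asks only that it come before therapy.
- Weeks 4 and 8: counted from the start of therapy (payment schedule and Procedures).
- Week 12: counted from the start of therapy (Procedures).
- SAP: four fixed time levels with no origin.

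For a student who starts on date S, the assessments fall due at S + 4, S + 8 and S + 12 weeks. For a student who never starts, S does not exist and neither do the due dates. That student has a baseline score but no scheduled post-baseline score. A conventional repeated measures ANOVA needs all four levels and would drop the student.

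**2. Comparing starters only**

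Let shares a and b of the two arms never start, and let non-starters end d points worse than starters in the same arm. The mean over all assigned students is then worse than the starters' mean by a × d in one arm and b × d in the other. Restricting to starters shifts the between-arm difference by

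(a − b) × d, towards the arm with more non-starters.

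- 10% vs 5%, d = 2: 0.05 × 2 = 0.1 PHQ-9 points.
- 20% vs 10%, d = 3: 0.10 × 3 = 0.3 points.
- 30% vs 10%, d = 4: 0.20 × 4 = 0.8 points.
- Equal rates and equal d: 0.

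Swapping the arms reverses the sign.

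**3. Unequal intervals**

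Suppose one arm waits w weeks longer than the other, and the other starts at once with baseline taken at assignment.

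| Extra wait w (assumed) | Baseline to week 4 | Baseline to week 12 |
|---|---|---|
| 0 | 4 weeks | 12 weeks |
| 1 week | 5 weeks (+25%) | 13 weeks (+8%) |
| 2 weeks | 6 weeks (+50%) | 14 weeks (+17%) |
| 4 weeks | 8 weeks (+100%) | 16 weeks (+33%) |

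If symptoms drift by r points a week for reasons other than therapy, the between-arm change moves by r × w. With r from 0.05 to 0.2 and w from 1 to 4, that is 0.05 × 1 = 0.05 to 0.2 × 4 = 0.8 points. The sign depends on which arm waits longer and on whether symptoms ease or worsen meanwhile.

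**4. Precision**

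With 100 per arm (assumed), the difference detectable with 80% power at two-sided 0.05 is (1.96 + 0.84) × √(2/100) = 0.40 SD in a simple comparison of two means. If 5% to 30% never start, n per arm falls to 95 to 70 and the figure rises to 0.41 to 0.47 SD. The loss of precision is modest; the change in who is compared matters more.

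**The case against.** A reader might infer that only the group arm waits, because a group needs peers before it exists, and might try to estimate the wait from the maximum of 200 and the project dates. The documents do not support this. The phrase "asynchronous communication with peers struggling with similar issues" describes the support given and is not an admission rule. No group size, closed cohort or waiting period is stated, and rolling entry to an asynchronous text group fits the text equally well. The dates 8/2024 to 8/2028 are the project period, not an accrual window, and recruitment begins with an email to all students, which could bring entries in clusters. Individual therapy needs one counselor per student, and the Purpose of Study section itself says therapists are too few, so those students could wait as well.

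A reader might also infer that the error must favour the group arm. That requires more non-starters or longer waits in that arm, together with worse outcomes among non-starters or improvement while waiting. No figure in the documents shows any of these.

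The 12-week cap on participation suggests that no long gap is planned, in which case the two clocks nearly coincide for those who start. It does nothing for those who never start. The documents also do not say that non-starters will be left out of follow-up. They are silent, and the Qualtrics surveys do not depend on logging in to therapy. But the only schedule given produces no due date for them.

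A likelihood-based mixed model would keep non-starters' baseline scores and is valid if data are missing at random. The SAP does not plan one. With no follow-up from any non-starter, that assumption could not be checked.

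Finally, anchoring at start and anchoring at assignment answer different questions, and the assignment clock disadvantages an arm that starts late. That trade-off is real and is carried into the fix.

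**Conclusion.** The concern holds in a limited form. Follow-up is counted from the start of therapy, the gap from baseline to start is unlimited, and a student who is assigned but never starts has no scheduled post-baseline PHQ-9 or GAD-7. Under the planned ANOVA the comparison is then among starters. Any difference between arms in time to start would also make the baseline-to-week-12 intervals unequal.

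The size and direction cannot be determined from the documents. The range of 0.1 to 0.8 PHQ-9 points rests on assumed non-start rates 5 to 20 percentage points apart and an assumed gap of 2 to 4 points. It points towards whichever arm has more non-starters, and vanishes if rates and gaps are equal. A wait confined to the group arm, and a bias necessarily in its favour, are not established. The gap is nevertheless more than missing detail, because it decides which data are collected.

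**What to change.** - In the Procedures and the payment schedule, state that PHQ-9 and GAD-7 are due from every assigned student, and that the surveys are sent and paid for whether or not therapy has started or continues.
- Date weeks 4, 8 and 12 from assignment for the primary PHQ-9 and GAD-7 comparison. At the least, give students who do not start due dates counted from assignment.
- Record assignment and therapy start dates, and report the start rate and delay by arm.
- State in the SAP what the weeks are counted from, and that PHQ-9 and GAD-7 are analysed by assigned arm.
- Keep the engagement and experience items for students who used the service, since others cannot answer them.
- Reconcile the schedule with the 12-week cap on participation.

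This is practicable: the scales are collected in Qualtrics, separately from the platform's log data, and the amended procedures collect an email address at entry.

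Cost: an IRB wording amendment and short SAP text. Gift cards come to at most 305 − 5 = $300 per non-starter who completes all three follow-ups. If 10% of 200 never start (assumed) and all respond, that is 20 × 300 = $6,000. On the assignment clock, students who start late will have had less than 12 weeks of therapy at week 12, so the delay by arm should be reported beside the result.
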